#### **6.1.1.4. Rilpivirine Extended Release Suspension for Injection (RPV LA)**

RPV LA (TMC278, GSK1329758, also named JNJ-16150108-AAA), 300 mg/mL Extended Release Suspension for Injection (G001), is provided by Janssen Research & Development, LLC, a division of Janssen Pharmaceuticals, as a sterile white suspension containing 300 mg/mL of RPV as the free base. The route of administration is by intramuscular (IM) injection. RPV LA is packaged in a single use 4 mL glass vial with a 13 mm stopper and aluminum seal. Each vial contains a nominal fill of 2.0 mL (600 mg) and does not require dilution prior to administration. The recommended storage conditions, and expiry date where required, are stated on the product label.

RPV LA is composed of RPV free base, poloxamer 338, sodium dihydrogen phosphate monohydrate, citric acid monohydrate, glucose monohydrate, sodium hydroxide, water for injection.

## **6.2. Preparation/Handling/Storage/Accountability**

The investigator or designee must confirm appropriate temperature conditions have been maintained during transit for all study intervention received and any discrepancies are reported and resolved before use of the study intervention.

Only participants enrolled in the study will receive study intervention and only authorized site staff may supply or administer study intervention. All study interventions must be stored in a secure, environmentally controlled, and monitored (manual or automated) area in accordance with the labeled storage conditions with access limited to the investigator and authorized site staff.

The investigator, institution, or the head of the medical institution (where applicable) is responsible for study intervention accountability, reconciliation, and record maintenance (i.e., receipt, reconciliation, and final disposition records).

Further guidance and information for the final disposition of unused study intervention are provided in the Study Reference Manual (SRM).

- Under normal conditions of handling and administration, study intervention is not expected to pose significant safety risks to site staff. Take adequate precautions to avoid direct eye or skin contact and the generation of aerosols or mists. In the case of unintentional occupational exposure notify the monitor, Medical Monitor and/or GSK/ViiV study contact.
- Precaution will be taken to avoid direct contact with the study intervention. A Material Safety Data Sheet (MSDS) describing occupational hazards and recommended handling precautions will be provided to the investigator. In the case of unintentional occupational exposure notify the monitor, Medical Monitor and/or GSK/ViiV study contact.

#### **6.2.1. Dosing Considerations for CAB LA + RPV LA**

Vials of CAB LA and RPV LA are each supplied as a suspension and need no further dilution or reconstitution. Since RPV LA requires refrigeration, sites should allow the vial(s) to come to approximately room temperature prior to injecting. The vials should be gently inverted a few times to re-suspend sediments and allow bubbles to subside, and then use a syringe or provided vial adapter to withdraw the required volume of suspension for IM injection.

All injections must be given intramuscularly in the thigh muscle, each injection on one thigh. The time and location of injection will be captured in the case report form (CRF).

Additional injections instructions can be found in the SRM.

#### **6.3. Study Intervention Compliance**

- When participants are dosed at the site, they will receive study intervention directly from the investigator or designee, under medical supervision. The date and time of each dose administered in the clinic will be recorded in the source documents. The dose of study intervention and study participant identification will be confirmed at the time of dosing by a member of the study site staff other than the person administering the study intervention. Study site personnel will examine each participant's mouth to ensure that the study intervention was ingested.
- When participants self-administer study intervention(s) at home, compliance with CAB + RPV dosing will be assessed through querying the participant during the site visits and documented in the source documents and CRF. IP accountability will be evaluated using pill counts of unused IP (CAB and RPV tablets).
- A record of the number of CAB + RPV tablets dispensed to and taken by each participant must be maintained and reconciled with study intervention and compliance records. Intervention start and stop dates, including dates for intervention delays and/or dose reductions will also be recorded in the CRF.

#### **6.4. Concomitant Therapy**

Any medication or vaccine (including over-the-counter or prescription medicines, vitamins, and/or herbal supplements or other specific categories of interest) that the

participant is receiving at the time of enrollment or receives during the study must be recorded along with:

- reason for use
- dates of administration including start and end dates
- dosage information including dose and frequency

The Medical Monitor should be contacted if there are any questions regarding concomitant or prior therapy.

#### **6.4.1. Permitted Medications and Non-Drug Therapies**

Participants must abstain from taking prescription drugs within 7 days (or 14 days if the drug is a potential enzyme inducer) or 5 half-lives (whichever is longer) before the start of study intervention until completion of the follow-up visit, unless, in the opinion of the investigator and sponsor, the medication will not interfere with the study.

Participants must abstain from taking non-prescription drugs (including vitamins and dietary or herbal supplements) within 7 days (or 14 days if the drug is a potential enzyme inducer) or 5 half-lives (whichever is longer) before the start of study intervention until the last PK sample collected on Week 8, unless, in the opinion of the investigator and sponsor, the medication will not interfere with the study.

Paracetamol/Acetaminophen at doses of  $\leq$  2 grams/day is permitted for use any time during the study. Other concomitant medication may be considered on a case-by-case basis by the investigator in consultation with the Medical Monitor if required.

##### **Oral CAB and RPV only:**

- Antacid products containing divalent cations (e.g., aluminum, calcium and magnesium) must be taken at least 2 hours before or at least 4 hours after oral CAB and RPV
- H2 antagonists must be taken at least 12 hours before or at least 4 hours after oral RPV oral RPV should not be co-administered with proton pump inhibitors, such as esomeprazole, lansoprazole, omeprazole, pantoprazole, rabeprazole

#### **6.4.2. Prohibited Medications and Non-Drug Therapies**

For participants receiving **either formulation** of CAB and RPV, the following medications could significantly decrease the levels of CAB and/or RPV due to enzyme induction and therefore must not be administered concurrently:

- Carbamazepine
- Oxcarbazepine
- Phenobarbital
- Phenytoin
- Rifabutin
- Rifampicin/ rifampin, rifapentine

- Rifapentine
- St. John's wort (*Hypericum perforatum*)

In addition, participants must discontinue the following (or change to an allowable alternative) while receiving treatment with oral RPV:

- proton pump inhibitors, such as esomeprazole, lansoprazole, omeprazole, pantoprazole, rabeprazole;
- systemic dexamethasone (more than a single dose).
- anticonvulsants carbamazepine, oxcarbazepine, phenobarbital, phenytoin.

The sponsor must be notified in advance (or as soon as possible thereafter) of any instances in which prohibited therapies are administered.

## **6.5. Dose Modification**

No dose reductions, modifications, or changes in the frequency of any components of each regimen will be allowed during the study beyond what is allowed within the protocol. Protocol waivers or exemptions are not allowed. Therefore, adherence to the study design requirements is essential and required for study conduct.

## **6.6. Intervention after the End of the Study**

Participants will not receive any additional treatment from GSK/ViiV Healthcare after completion of the study because only healthy participants are eligible for study participation.

# **7. DISCONTINUATION OF STUDY INTERVENTION AND PARTICIPANT DISCONTINUATION/WITHDRAWAL**

## **7.1. Discontinuation of Study Intervention**

Participants may voluntarily withdraw from the study at any time and for any reason. Site investigators and study staff may withdraw participants before their scheduled termination visit for safety, behavioral, or administrative reasons, or if the participants are unable or unwilling to comply with study procedures. The reasons for withdrawals will be recorded in the participants' study records. If a participant withdraws from the study, he/she may request destruction of any samples taken, and the investigator must document this in the site study records.

During the oral lead-in period, early withdrawal on medical grounds will occur if the participant develops a Grade 3 or higher AE that is judged by the investigator to be related directly to the study product (see [Appendix 3](#) and [Appendix 4](#) for definitions and grading of severity of adverse events), or a participant develops a grade 3 or higher clinical significant laboratory abnormality (see Division of AIDS [DAIDS] table [Appendix 7](#) for grading) or any AE that is deemed clinically significant by the investigator and is judged by the investigator to be related directly to the study product.

For liver-related stopping criteria, please refer to Section [7.1.1](#).

If a participant receives the injections, they will be followed 52-weeks post the final injection per protocol for appropriate procedures, including blood plasma PK sampling, and safety evaluations, and will not be removed from the study for medical reasons, unless they refuse to continue participation.

[figure not shown]
During the oral lead in phase additional pre-specified reasons for discontinuing a participant from the study (or, at minimum, discontinuing administration of study product and continuing safety evaluations) include:

- Pregnancy (please see Section 8.2.5)
- Protocol deviation
- Non-compliance
- Participant withdraws consent
- Participant lost to follow-up
- Investigator discretion
- Sponsor discontinues study

### **7.1.1. Liver Chemistry Stopping Criteria**

Study intervention will be discontinued **for a participant** if liver chemistry stopping criteria are met:

## Phase I Liver Chemistry Stopping Criteria – Liver Stopping Event Algorithm

Abbreviations: ALT = alanine transaminase; INR = international normalized ratio; SAE = serious adverse event; ULN = upper limit of normal.

**Liver chemistry stopping and increased monitoring criteria** have been designed to assure participant safety and evaluate liver event etiology (in alignment with the FDA premarketing clinical liver safety guidance).

<http://www.fda.gov/downloads/Drugs/GuidanceComplianceRegulatoryInformation/Guidances/UCM174090.pdf>

Discontinuation of study treatment for abnormal liver tests should be considered by the investigator when a participant meets one of the conditions outlined or if the investigator believes that it is in the best interest of the participant.

Refer to [Appendix 6](#) for required Liver Safety Actions and Follow up Assessments.

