## NOTES:

1. An overnight fast is preferred prior to screening laboratory assessments; however, a minimum of a 6 hour fast is acceptable.
2. Details of liver chemistry stopping criteria and required actions and follow-up assessments after liver stopping or monitoring event are given in Section 7.1 and [Appendix 7](#) All events of  $ALT \geq 3 \times$  upper limit of normal (ULN) and bilirubin  $\geq 2 \times$  ULN ( $>35\%$  direct bilirubin) or  $ALT \geq 3 \times$  ULN and international normalized ratio (INR)  $>1.5$ , if INR measured, which may indicate severe liver injury (possible Hy's Law), must be reported as an SAE (excluding studies of hepatic impairment or cirrhosis).
3. Local urine testing will be standard for the protocol unless serum testing is required by local regulation or IRB/IEC.

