## 11.6. Appendix 6: Liver Safety: Required Actions and Follow-up Assessments

Phase 1 liver chemistry stopping criteria have been designed to assure participant safety and to evaluate liver event etiology

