### Phase 1 liver chemistry stopping criteria and required follow up assessments

Liver Chemistry Stopping Criteria	
ALT-absolute ALT $\geq$ 3xULN If ALT $\geq$ 3xULN AND bilirubin  $\geq$ 2xULN (>35% direct bilirubin) or international normalized ratio (INR) $>1.5$ , Report as an SAE. See additional Actions and Follow Up Assessments listed below	
Required Actions and Follow up Assessments	
Actions	Follow Up Assessments

 
• Immediately discontinue study intervention
 
• Report the event to GSK within 24 hours
 
• Complete the liver event CRF, and complete an SAE data collection tool if the event also meets the criteria for an SAE
 
• Perform liver event follow up assessments
 
• Monitor the participant until liver chemistries resolve, stabilize, or return to within baseline (see MONITORING below)
 
 
MONITORING:
 
If ALT<math>\geq</math>3xULN AND bilirubin <math>\geq</math> 2xULN or INR <math>>1.5</math>
 
 
• Repeat liver chemistries (include ALT, aspartate transaminase [AST], alkaline phosphatase, bilirubin and INR) and perform liver event follow up assessments within 24 hours
 
• Monitor participant twice weekly until liver chemistries resolve, stabilise or return to within baseline
 
• A specialist or hepatology consultation is recommended
 
	
 
• Viral hepatitis serology
 
• Obtain INR and recheck with each liver chemistry assessment until the transaminases values show downward trend
 
• Obtain blood sample for pharmacokinetic (PK) analysis, obtained CAB + RPV of last dose
 
• Serum creatine phosphokinase (CPK) and lactate dehydrogenase (LDH).
 
• Fractionate bilirubin, if total bilirubin<math>\geq</math>2xULN
 
• Obtain complete blood count with differential to assess eosinophilia
 
• Record the appearance or worsening of clinical symptoms of liver injury, or hypersensitivity, on the AE report form
 
• Record use of concomitant medications on the concomitant medications report form including acetaminophen, herbal remedies, other over the counter medications.
 
• Record alcohol use on the liver event alcohol intake CRF
 

Liver Chemistry Stopping Criteria	

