### 11.4.4. Reporting Standards for Liver Safety Data

#### 11.4.4.1. Liver Stopping/Monitoring Criteria

Element	Reporting Detail
General	
 
A liver monitoring event occurs when subject meets predefined liver chemistry monitoring criteria that trigger increased monitoring of the subject's liver chemistries, but no action is taken with study treatment unless liver chemistry stopping criteria are
 

Element	Reporting Detail
	
met. A liver stopping event occurs when subject meets predefined liver chemistry stopping criteria, ALT <math>\geq 3 \times \text{ULN}</math> for this study, that trigger discontinuation of study treatment and requirement of additional actions and follow up assessments to be performed. For subjects with more than one liver stopping or liver monitoring event, only data related to the earliest most severe criteria event is included in displays.
 
 
Resolved is defined as ALT <math>< 3 \times \text{ULN}</math> for 2 consecutive visits or <math>< 3 \times \text{ULN}</math> for one visit if subject discontinued and no data available. Post treatment records are included to evaluate resolution of the event.
 

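### Protocol 7.1.1 makes the liver stop mandatory in one sentence and discretionary in another; the discretionary sentence is wrong for any participant who meets the stopping criterion

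*Protocol*

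**What the plan says.** Section 7.1 of the protocol hands the liver question to one place: "For liver-related stopping criteria, please refer to Section" 7.1.1. The drug-induced liver injury row of the risk table (Section 2.3.1) also names 7.1.1 as the mitigation.

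Section 7.1.1 then says two things. Its opening sentence is an obligation that applies when the stopping criteria are met: "Study intervention will be discontinued". Under the subheading for the liver stopping event algorithm, it says: "Discontinuation of study treatment for abnormal liver tests should be considered by the investigator when a participant meets one of the conditions outlined". That sentence goes on to allow a stop whenever the investigator judges it best for the participant. The next sentence points to Appendix 6 for required actions.

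Appendix 6 sets the criterion at ALT ≥3xULN. Its first required action is to "discontinue study intervention", immediately.

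SAP 11.4.4.1 uses the same ALT threshold and describes a stopping event as meeting criteria "that trigger discontinuation of study treatment".

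Note 2 of Appendix 2 says that "required actions and follow-up assessments after liver stopping or monitoring event are given in Section 7.1 and" Appendix 7. Appendix 7 is the Division of AIDS severity grading table. The liver actions are under "Appendix 6: Liver Safety: Required Actions and Follow-up Assessments".

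**The concern.** Drug-induced liver injury is the first risk in the protocol's risk table. That table says every suspected case so far arose in participants taking oral CAB, and that the unexplained cases resolved when CAB was withdrawn. The oral lead-in is therefore the period in which a prompt stop matters most.

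An investigator who finds ALT ≥3xULN during the lead-in and turns to 7.1.1, as instructed, reads first that the drug will be stopped and then that stopping should be considered. Acting on the second sentence would keep the participant on both oral drugs when Appendix 6 requires an immediate stop. The next rule in the protocol, the QTc rule in 7.1.2, is written as mandatory withdrawal with no such softening.

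The wrong appendix number adds a small obstacle: a reader who starts from the laboratory appendix is sent to a grading table.

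**Working it through.** There is no plan figure to reproduce. The check sets the texts side by side and then makes one calendar count.

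**Status of the stop once the criterion is met**

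| Place | Status of the stop |
|---|---|
| Protocol 7.1.1, opening sentence | Mandatory |
| Protocol Appendix 6, first required action | Mandatory and immediate, at ALT ≥3xULN |
| Protocol 2.3.1, liver injury row | Treated as binding: participants are described as withdrawn because they met the criteria |
| SAP 11.4.4.1 | Criterion triggers discontinuation, same threshold (a reporting definition) |
| Protocol 7.1.1, under the algorithm heading | To be considered by the investigator |

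Four statements treat the stop as binding and one does not.

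**Which part of the discretionary sentence conflicts**

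1. The sentence has two limbs. One applies when a participant meets a listed condition. The other applies when the investigator thinks stopping is best for the participant.
2. The second limb is compatible with a mandatory stop, because it only adds reasons to stop.
3. The first limb conflicts. It stands under a heading about stopping criteria and is not limited to results below the threshold, so it covers a participant at ALT ≥3xULN. For that participant it says consider, while the opening sentence and Appendix 6 say stop.

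**Calendar count of oral doses at stake**

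Inputs, from the protocol schedule of activities: oral dosing on Days 1 to 28; chemistry after the first oral dose and before the injection visit on Days 2, 14 and 29. The Day 1 sample is drawn before dosing and is not counted.

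If the result is known after that day's dose, the doses remaining are 28 minus the sampling day:
- Day 2: 28 − 2 = 26
- Day 14: 28 − 14 = 14
- Day 29: dosing has ended, so 0

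If the result is known before that day's dose, add one while dosing continues: 27, 15 and 0. Under Appendix 6 no dose follows the result in any of these cases.

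These are nominal-day upper bounds. They assume that the participant is kept on treatment to Day 28 and that no other rule intervenes.

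**The case against.** The strongest objection is that the algorithm figure is missing from the text available for review, so the conditions it lists cannot be seen. The sentence just before the disputed one speaks of increased monitoring criteria as well as stopping criteria, and Appendix 2 note 2 mentions monitoring events. If the figure includes monitoring-level conditions, telling the investigator to consider stopping would be reasonable for those. This stands as far as it goes. A reader might be tempted to close it off with SAP 11.4.4.1, which says that for a monitoring event "no action is taken with study treatment unless liver chemistry stopping criteria are" met. That inference is too strong: the SAP text sits under reporting standards and does not direct investigators, so it supports the ALT ≥3xULN threshold but does not exclude a meaning below it. The conflict does not depend on excluding that meaning. Even if the figure lists lower conditions, the sentence as worded still covers the participant who meets the stopping criterion.

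The second objection is that the protocol already corrects itself. Section 7.1.1 opens with the obligation and refers to Appendix 6 straight after the disputed sentence. Appendix 6 requires a report to the sponsor within 24 hours and repeat chemistries within 24 hours or 24 to 72 hours, depending on bilirubin and INR. Section 8 asks for safety concerns to be discussed with the sponsor immediately. A careful investigator would probably follow the stricter text. All of this stands and limits the practical reach, but a stopping rule should not leave the reader to decide which of two sentences prevails.

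The general lead-in rule in Section 7.1, withdrawal for a clinically significant laboratory abnormality of Grade 3 or higher, is only a partial backstop. The documents as available do not show which ALT multiple is Grade 3, and clinical significance is itself a judgement.

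The wrong appendix number has little consequence alone, because the same note also names Section 7.1, which leads to 7.1.1 and from there to Appendix 6.

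**Conclusion.** Section 7.1.1 is internally inconsistent, and the discretionary sentence is wrong as written for any participant with ALT ≥3xULN. This rests on two things: Appendix 6 states the criterion that 7.1.1 invokes, and the algorithm's conditions include that criterion, as its title indicates.

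The size is small. The exposure is participant safety in the 28-day oral lead-in. No PK endpoint, estimate or sample-size argument is touched, and the binding rule can be recovered from the opening of 7.1.1, Appendix 6 and the risk table. The threshold itself is not in dispute.

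Two stronger readings are not supported. A reader might take the dose counts as an expected harm. They are calendar maxima, and the documents give no event rate to attach to them. A reader might also infer that a participant who meets the criterion in the lead-in could still receive the long-acting injections. Section 6 includes CAB LA and RPV LA in the investigational product, the risk table treats meeting the criteria as withdrawal, Section 7.2 makes discontinuation permanent on withdrawal from the study, and Section 4.1.1 bars re-screening after withdrawal. Together these imply that the injections are not given.

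**What to change.** In Protocol 7.1.1, replace the discretionary sentence with: *Study intervention must be discontinued when a participant meets the liver stopping criterion (ALT ≥3xULN). The investigator may also discontinue study intervention for other liver abnormalities when that is in the participant's best interest.* The second sentence keeps the discretion that Sections 7.1 and 7.1.1 already give.

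In Appendix 2 note 2, change Appendix 7 to Appendix 6.

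When making the edit, the sponsor should check that the algorithm figure agrees with the new wording.

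The cost is one sentence and one cross-reference in the protocol. No assessment is added, no analysis changes, and the SAP can stay as it is because 11.4.4.1 already uses ALT ≥3xULN as the stopping criterion.
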